## **2.1 End points**

- **Primary**  
2-year progression free survival
- **Secondary**  
Metabolic response rate  
Overall survival  
Toxicity level (CTCAE version 4.03)

## **3.0 Investigational plan**

### **3.1 Overall design**

This is a single arm phase II study to assess the safety, efficacy and toxicity of carboplatin AUC-10 in metastatic seminoma. Patients will be recruited from two sites.

Prior to the commencement of treatment, the patient should have a baseline PET-CT scan and a contrast enhanced CT scan performed within 28 days of study entry. Patients will be treated with carboplatin AUC-10 every 3 weeks (3 weeks=1 cycle) and on day 17-21 of the first cycle a repeat PET-CT scan will be performed. All PET-CT scans will be reviewed centrally and these results will determine how many further treatment cycles the patients will undergo. If the patient has a complete metabolic response [refer to Appendix 3], a further 2 cycles of carboplatin will be given, leading to a total of 3, and if the patient has not had a complete metabolic response but is responding, a further 3 cycles of carboplatin will be given [Refer to section 5.3.3 and page 20 (the table) for the timelines for the scans. Please refer to appendix 8 for the imaging protocol].

If no response is seen, then the patient will be taken off study and will receive conventional therapy using a cisplatin-based combination.

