#### **4.4 *Withdrawal of subjects***

Patients will be informed that they have the right to withdraw from the study at any time, for any reason, without prejudice to their medical care. The primary reason (if available) for a patient's withdrawal from the study should be recorded on the case report form (CRF). The right of patients to refuse to participate without giving reasons and prejudicing their further treatment will be respected. Any patients who decide to withdraw their consent completely will have no further data collected. However, if the patient withdraws from trial treatment only their data may be followed-up for survival as long as the patient is happy to do so.

The investigator also has the right to withdraw patients from the study for any of the following reasons:

- Disease Progression.
- Occurrence of intolerable side effects.
- Non-compliance.
- A delay in treatment of 14 days or more.

At the time of withdrawal, all end of study procedures should be completed (as per schedule of assessments). The patient will remain in the study for the purposes of follow up and data analysis.

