##### **4.4.1 *Data collection and follow up for withdrawn subjects***

CRFs should be sent to the Centre for Experimental Cancer Medicine, Barts Cancer Institute within one month of patient completing each cycle.

Subjects who are withdrawn are still evaluable for toxicity and efficacy if they have received at least one cycle of treatment and any data collected whilst receiving treatment will be used in the final analysis. Patients who are withdrawn from the study will be followed up for 2 years after treatment. Similarly, this follow up data will be used in the

final analysis. Any patients who decide to withdraw their consent will have no further data collected unless they have given express permission to do so.

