### **11.5 Primary endpoint analysis**

The primary efficacy endpoint is Progression Free Survival (PFS) rate at 2 years. Patients who do not complete 2 years follow-up for reasons other than death will be censored at the last date of follow-up. The PFS rate will be determined for the Carboplatin AUC-10, along with a 95% confidence interval, and the Kaplan-Meier curves will be plotted. The study result will be considered positive if the PFS rate for patients on Carboplatin AUC-10 is consistent with a true difference of 15% or more from standard chemo i.e. if there are at least 39 PFS patients out of the first 45 patients at 2 years.

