3.1 General Study Design and Plan

This is a single arm phase II study to assess the safety, efficacy and toxicity of carboplatin AUC-10 in metastatic seminoma. Up to 50 patients will be recruited into the study over four years (assuming 5 patients may drop out for reasons other than disease progression/intolerable side effects). 45 evaluable patients will be necessary to establish activity of carboplatin AUC10 in this setting. Patients will be recruited for 48 months. Patients will be followed up as part of the study for 2 years following completion of treatment. The end of the study will be 3 months after the date when the last patient has completed his final follow up visit.

Prior to the commencement of treatment, the patient should have a baseline PET-CT scan and a contrast enhanced CT scan performed within 28 days of study entry. Patients will be treated with carboplatin AUC-10 every 3 weeks (3 weeks=1 cycle) and on day 17-21 of the first cycle a repeat PET-CT scan will be performed. If the patient has a complete metabolic response (see Appendix 3 of the protocol), a further 2 cycles of carboplatin will be given, leading to a total of 3, and if the patient has not had a complete metabolic response but is responding, a further 3 cycles of carboplatin will be given.

If a patient is showing no response to treatment then the patient will be taken off study and will receive conventional therapy using a cisplatin-based combination.

Figure 1: Treatment Flowchart

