3.4 Study Variables

3.4.1 Primary and Secondary Variables

3.4.1.1 Primary Efficacy Variables

3.4.1.1.1 Progression-Free Survival (PFS)

PFS is defined as the time between the date of enrolment to first evidence of disease progression based on central review or death, whichever occurs first. For patients who have not died or experienced disease progression at the end of study, PFS will be censored on the last date the patient was known to be progression-free. Patients with no post-baseline tumour assessment will be censored at the date of enrolment plus 1 day. The PFS time will always be derived based on scan/assessment dates not visit dates.

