5.2.1.1 Full Analysis Set (FAS) population

The FAS will consist of all patients who completed at least one cycle of carboplatin AUC-10 and for whom relevant data is available at baseline and follow up. All efficacy analyses will be performed on the FAS population.

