7.2 Primary Efficacy Analysis

7.2.1 PFS

Kaplan-Meier (K-M) methodology will be used to estimate the median PFS. The median PFS and PFS rate for carboplatin AUC-10 at 2-years will be estimated with one-sided 95% CI to be consistent with one-sided test. However, 2-sided 95% CI will also be presented. The study result will be considered positive if the PFS rate for patients on carboplatin AUC-10 is consistent with a true difference of 15% or more from standard chemo i.e. if there are at least 39 PFS patients out of the first 45 patients at 2 years.

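### Read literally, the PFS rule can count a patient switched to cisplatin-based therapy for no response among the 39 of 45 AUC-10 successes, and the plan does not settle how he is counted

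*Protocol*

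**What the plan says.** **The switch.** Protocol 3.1 directs: "If no response is seen, then the patient will be taken off study and will receive conventional therapy using a cisplatin-based combination". SAP 3.1 repeats it: "If a patient is showing no response to treatment then the patient will be taken off study and will receive conventional therapy".

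**The endpoint.** SAP 3.4.1.1.1 states: "PFS is defined as the time between the date of enrolment to first evidence of disease progression based on central review or death". A patient without an event is censored when last known to be progression-free. Neither non-response nor the start of another treatment is an event or a reason for censoring, here or in Protocol 11.5.

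**Who stays in.** Protocol 4.4 says of withdrawn patients: "The patient will remain in the study for the purposes of follow up and data analysis". Protocol 4.4.1 adds: "Subjects who are withdrawn are still evaluable for toxicity and efficacy if they have received at least one cycle of treatment", with 2 years of follow-up that enters the final analysis. The FAS in SAP 5.2.1.1 covers "all patients who completed at least one cycle of carboplatin AUC-10", provided that relevant baseline and follow-up data exist.

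**The decision.** Protocol 11.5 calls the result positive "if the PFS rate for patients on Carboplatin AUC-10 is consistent with a true difference of 15% or more from standard chemo", which SAP 7.2.1 makes operational as "if there are at least 39 PFS patients out of the first 45 patients at 2 years". Protocol 11.2.1 sets the question as whether AUC-10 merits a phase III study.

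**Further therapy.** Protocol 5.5 requires any later seminoma treatment to be recorded on the CRF. No analysis rule uses that record.

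**The concern.** The success rule is worded for patients on AUC-10 and compares them with standard chemotherapy, which Protocol 1.1 describes as cisplatin-based. A patient who did not respond to one cycle of AUC-10, had not progressed, and then did well on a cisplatin-based combination meets the literal definition of a progression-free patient. His success owes something, perhaps everything, to the benchmark type of treatment, and a single-arm design cannot separate the two contributions.

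The cut-off has no slack, so one patient can decide the conclusion. If the counting rule stays open until the data are in, it may be chosen with the count known.

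**Working it through.** **1. Reproduce the design.** Inputs from Protocol 11.2.1: null rate 75%, target 90%, one-sided 5%, power 80%. With X binomial(45, p):
- P(X ≥ 39 | p = 0.75) = 0.0446
- P(X ≥ 39 | p = 0.90) = 0.8415

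45 is the smallest sample size that meets both limits, and 45/(1 − 0.10) = 50. The stated design reproduces. The point concerns what counts as a success, not the arithmetic.

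**2. Can the patient exist?** Appendix 2 of the protocol makes stable disease a category separate from progression, so non-response without progression is a defined state. A non-responder classed as progressive is already a failure and is outside this point.

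**3. How could he be counted?**

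| Reading | Basis | Effect on the count |
|---|---|---|
| Success if progression-free at 2 years | SAP 3.4.1.1.1; Protocol 4.4 and 4.4.1; SAP 5.2.1.1 | One of the 39 |
| Censored | Off-study instruction (Protocol 3.1, SAP 3.1), if it ends follow-up | Not defined for a count out of 45 |
| Outside the FAS | Follow-up data requirement in SAP 5.2.1.1 | Not among the 45 |
| Replaced | Synopsis and Protocol 3.4: 5 losses allowed for reasons other than progression | Not among the 45 |

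The first reading is the most literal. Against it, no response is not among the investigator's withdrawal reasons in Protocol 4.4. Protocol 5.3.2 and footnote 4 of the 5.4 flowchart also give every patient without a complete response 3 more cycles, with no exit for non-response.

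**4. What one patient does.** Exact (Clopper-Pearson) one-sided 95% lower limits:
- 38/45 = 84.4%, lower limit 72.8%, below the 75% bar: negative
- 39/45 = 86.7%, lower limit 75.4%: positive

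A single switched patient is decisive when exactly 38 of the other 44 are progression-free. P(X = 38 | n = 44, p) is 3.1%, 16.7% and 12.9% for p = 75%, 85% and 90%.

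**5. Chance of a positive result with k switched patients.** The documents give no k. Assume k = 1 or 2, all progression-free at 2 years. Counted as successes: P(X ≥ 39 − k | n = 45 − k, p). Counted as failures: P(X ≥ 39 | n = 45 − k, p).

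| k | Others at 75%: success / failure | Others at 90%: success / failure |
|---|---|---|
| 0 | 4.5% | 84.1% |
| 1 | 5.2% / 2.1% | 85.4% / 72.6% |
| 2 | 6.1% / 0.9% | 86.7% / 56.7% |

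**6. A different assumption.** Suppose instead that 75% is the success rate without any switched patients' successes, and that a share s of all patients switch and succeed at 81% (the BEP figure in Protocol 11.2.1). The counted rate is then 0.75 + 0.81s:
- s = 1/45: 0.768, chance of a positive result 7.6%
- s = 2/45: 0.786, chance 12.5%

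The size therefore depends on the assumption as well as on the unknown number.

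**The case against.** **The documents do not plainly count him as a success.** A reader might infer that the plan fixes this. It does not: that reading needs the withdrawal sections to override the off-study instruction, and three other readings are open. If he is replaced, the rule keeps its 4.5% error and 84.1% power. This stands, and it limits the point to the most literal reading. Protocol 4.4.1, which keeps a patient evaluable after one cycle, weighs against replacement but does not settle it.

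**PFS regardless of later treatment is legitimate.** The trial's title describes therapy directed by the initial PET-CT response, and Protocol 11.2.1 defines the outcome as the percentage progression-free at 2 years. This also stands. A reader might infer that a switch must count as failure in the primary analysis. That would be a different endpoint from the one in SAP 3.4.1.1.1, and the documents do not require it. Nor do they support extending it to all further chemotherapy, which would draw in withdrawals for toxicity or delay.

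**Few patients will be affected.** Probably so. Protocol 1.3 reports 2 relapses in 40 AUC-10 patients and says that most patients in the earlier study eventually reached complete response, though this is only indirect evidence on non-response. Appendix 3 puts a marker fall of less than 50% under both stable and progressive disease, so some marker-defined non-responders may already be failures. This narrows the group without emptying it.

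**Any single reclassified patient moves 38 to 39.** True. Here, though, the protocol itself prescribes the event that leaves the classification open. The treatment flowcharts are not reproduced in the text reviewed and may show the no-response pathway.

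**Conclusion.** The point holds as an unsettled counting rule in the primary decision. On the most literal reading, a non-progressing non-responder who does well after cisplatin-based therapy is credited to AUC-10. Other passages would have him censored, excluded or replaced.

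A reader might infer that the 5% error rate is materially broken. The documents do not support that, because they give no number of switched patients. With 1 or 2 assumed, the false-positive chance goes from 4.5% to 5.2% or 6.1% on one model and to 7.6% or 12.5% on the other. What is certain is narrower: one such patient can carry the result across the line between 38 and 39. It is worth settling before analysis because the remedy is cheap, and confidence in its practical size is only moderate.

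**What to change.** Keep the PFS definition in SAP 3.4.1.1.1 as primary. Before analysis:

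1. State in SAP 3.4.1.1.1 and 7.2.1 that patients switched to cisplatin-based therapy for no response stay in the denominator of the first 45, and how one whose follow-up stops before 2 years is counted.
2. Pre-specify a sensitivity count in which patients switched for non-response before documented progression are not progression-free, with the denominator still 45.
3. List these patients, with reasons, from the further-therapy record required by Protocol 5.5.
4. If the two counts disagree about reaching 39, say so in the conclusion about AUC-10.
5. Reconcile the no-response text in Protocol 3.1 and SAP 3.1 with the Synopsis and Protocol 3.4, 4.4, 4.4.1, 5.3.2, 5.4 (footnote 4) and the stable and progressive categories of Appendix 3. This is a matter of consistent wording; it proposes no change to patient care.

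**Cost.** A short SAP addition, one extra count and one listing, from data already collected. The sensitivity count is less favourable. If the 90% target was meant to include rescued patients, and their share is assumed to be 2% or 5%, P(X ≥ 39 | n = 45) falls from 84.1% to 70.8% (p = 0.88) or 47.8% (p = 0.85). If 90% is already net of them, nothing is lost. The primary count's definition is unchanged.

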**All PET CT scans will be performed at (or sent to) University College Hospital to be centrally reviewed.**

### **3.2 Treatment plan**

Carboplatin will be administered as a day case and doses will be calculated using the Calvert formula as below:

$$\text{Dose (mg)} = (\text{GFR} + 25) \times 10$$

Unless dictated by haematological toxicity, the Carboplatin dose should not be recalculated for each cycle. However, if the serum Creatinine has risen by > 20% above baseline, the Carboplatin dose must be recalculated using the Calvert formula with GFR determined by EDTA clearance. At the discretion of the PI an estimated creatinine clearance can be calculated using e.g. Cockcroft and Gault (or as per local policy) if the site is unable to obtain EDTA clearance.

Treatment will be repeated every 3 weeks (when platelets over  $100 \times 10^9/L$ , white blood count greater than  $3 \times 10^9/L$  or neutrophils greater than  $1 \times 10^9/L$ ).

If the blood count is below the level required to commence the next cycle of treatment (i.e. platelets less than  $100 \times 10^9/L$ , white blood count less than  $3 \times 10^9/L$  or neutrophils less than  $1 \times 10^9/L$ ) then a further blood count must be repeated 48 hours after the target treatment day. If the results of this repeat count show platelets greater than  $75 \times 10^9/L$  and rising, white blood count greater than  $3 \times 10^9/L$  or the neutrophils greater than  $1 \times 10^9/L$  the patient may commence to the next cycle [See Figure 1].

If neutrophils are less than  $1 \times 10^9/L$  and white blood count less than  $3 \times 10^9/L$ , filgrastim or lenograstim (GCSF) should be given for 2 days.

However, if the blood count remains below the level required it should continue to be monitored at 48 hour intervals until it has reached the required level for proceeding with further treatment (platelets are greater than  $75 \times 10^9/L$  and rising, white count greater than  $3 \times 10^9/L$  or the neutrophils are greater than  $1 \times 10^9/L$ ).

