**Please note that a delay of 14 days or more will require the patient to be withdrawn from study.**

**If a patient is admitted with neutropenic sepsis, prophylactic antibiotics e.g. ciprofloxacin, day 10 – 21 (with or without filgrastim or lenograstim) should be used for all subsequent cycles.**

If the platelet nadir (day 13 -17) is less than  $20 \times 10^9/L$ , then a **20% dose reduction** should be made on subsequent administration of carboplatin.

Patients will be required to attend hospital to receive Carboplatin as a day case.

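### Protocol 3.2: the list that defines a low blood count is not the converse of the treat rule, so some counts both permit the next cycle and require a hold

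*Protocol*

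**What the plan says.** All of the text at issue is in Protocol 3.2, Treatment plan. Limits are in units of 10⁹/L.

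- **Treat rule.** "Treatment will be repeated every 3 weeks (when platelets over" 100, with white count above 3 "or neutrophils greater than" 1.
- **Hold rule.** "If the blood count is below the level required to commence the next cycle of treatment", which a bracketed list explains as platelets under 100, white count under 3 "or neutrophils less than" 1. The consequence is "then a further blood count must be repeated 48 hours after the target treatment day".
- **Re-check at 48 hours.** Treatment may start if platelets exceed 75 and are rising, with white count above 3 "or the neutrophils greater than" 1. The sentence on continued monitoring, at 48-hour intervals, uses the same test.
- **Growth factor.** "If neutrophils are less than" 1 *and* the white count is under 3, growth factor is given for two days.
- **Withdrawal.** 3.2 adds that "a delay of 14 days or more will require the patient to be withdrawn from study".

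Both 3.2 and 6.7 refer to Figure 1 for guidance. That figure was not available in the text I worked from.

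**The concern.** The bracketed list in the hold sentence is offered as a restatement of failing the treat rule. But the converse of *white count adequate or neutrophils adequate* is *both low*, whereas the list says *either low*. A patient whose two white-cell results disagree can therefore satisfy both sentences.

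This is an operative retreatment rule. Protocol 6.1 describes the drug as more toxic to bone marrow than cisplatin, and Protocol 1.2 mentions retreatment delays from myelosuppression with higher-dose carboplatin in another tumour type. In a multi-centre trial, two sites could each follow the written text and act differently on the same counts. What is directly at stake is the timing of individual cycles, which the SAP (6.5 Treatment Compliance) summarises as the median and range of cycle length.

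**Working it through.** The plan gives no figure to reproduce here; the check is one of logic.

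**Definitions, from Protocol 3.2.** P: platelets above 100. W: white count above 3. N: neutrophils above 1.

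- Treat = P and (W or N)
- Hold = not P, or not W, or not N

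**All eight combinations**

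| P | W | N | Treat rule met | Hold rule met |
|---|---|---|---|---|
| yes | yes | yes | yes | no |
| yes | yes | no | **yes** | **yes** |
| yes | no | yes | **yes** | **yes** |
| yes | no | no | no | yes |
| no | yes | yes | no | yes |
| no | yes | no | no | yes |
| no | no | yes | no | yes |
| no | no | no | no | yes |

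Both rules are met in 2 of 8 combinations, and neither rule in 0 of 8. Among the four combinations with adequate platelets, 2 conflict. With platelets below 100 the two rules agree.

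**Examples.** Platelets 120, white count 2.5, neutrophils 1.5: the treat rule is met because 1.5 > 1, and the hold rule is met because 2.5 < 3. Platelets 120, white count 3.5, neutrophils 0.8: the treat rule is met because 3.5 > 3, and the hold rule is met because 0.8 < 1.

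**Other readings of the lists.** A list of the form *A, B or C* can be read as A and (B or C), as any one of the three, or as (A and B) or C. Three readings of each rule give 3 × 3 = 9 pairings. The number of combinations meeting both rules is:

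| Treat rule read as | Hold: any one low | Hold: platelets low and (white count or neutrophils low) | Hold: (platelets and white count low) or neutrophils low |
|---|---|---|---|
| P and (W or N) | 2 | 0 | 1 |
| P or W or N | 6 | 2 | 4 |
| (P and W) or N | 4 | 1 | 2 |

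Eight of the nine pairings overlap. The one that does not leaves 2 of 8 combinations under neither rule: adequate platelets with both white-cell counts low, and low platelets with both adequate. No pairing that keeps *or* in both sentences makes them exact converses.

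**The other sentences in 3.2.** The re-check and continued-monitoring sentences use W or N, as the treat rule does. The growth-factor trigger is not W and not N, which is the exact negation of W or N. All three therefore agree with the treat rule on white cells, and the conflict lies between the treat rule and the hold list.

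**Length of a hold.** Take the first example and suppose the white-cell counts are unchanged at 48 hours. The white-cell part of the re-check is met (1.5 > 1), and platelets of 120 exceed 75. If platelets are rising, the patient is released after about 48 hours. If they are steady at 120, the patient fails a condition that the target-day rule does not contain, and the hold continues. Re-checks fall 2, 4, 6, 8, 10 and 12 days after the target day. All six would have to fail before the delay reached 14 days.

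**Side observation.** A value exactly at a limit (100, 3 or 1) is neither above nor below it, so the wording does not place it.

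**The case against.** The strongest reply is that the governing clause of the hold sentence refers back to the level just set. A patient who meets the treat rule is not below that level, so the bracketed list is only a loosely negated gloss. Three other sentences agree with the treat rule on white cells, and Figure 1, which the protocol names as the guide, may be clear. This has force. It locates the problem in one list set against one rule, and it means that the difference between *or* in the re-check and *and* in the growth-factor sentence is not a second inconsistency, although a reader might take it for one. It does not remove the conflict: the list states explicitly what counts as too low, and a site that applies it will hold. If Figure 1 is clear, the text still has to agree with it.

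The reply on consequences also largely stands. A hold on discordant white-cell counts ends at the first re-check if platelets are rising, and 48 hours lies within the ± 3 days allowed for Day 1 assessments of cycles 2 to 4 (Protocol 5.3.2 and 5.4). A reader might infer that the ambiguity drives 14-day withdrawals, or that delays and toxicity will reflect site habit. The documents do not show this. Reaching 14 days needs repeated failure of a re-check that has no competing list of low values, and nothing describes how sites behave. Nor is an effect on 2-year progression-free survival shown: under Protocol 4.4.1, withdrawn patients who received at least one cycle stay evaluable and are followed for two years.

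**Conclusion.** The concern holds as a contradiction between two adjacent statements in Protocol 3.2. On the ordinary reading, adequate platelets with exactly one of white count or neutrophils low meets both the treat rule and the hold rule: 2 of 8 combinations, or 2 of the 4 with adequate platelets. These are counts of logical cases, not of patients. The documents do not say how often the two white-cell results disagree when platelets are adequate, so the number of cycles affected cannot be derived.

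The direct consequence is that sites may treat or hold on identical counts. The resulting difference is about 48 hours if platelets are rising at the repeat count. A longer hold is possible because of the rising-platelet condition, with unknown frequency. The conclusion rests on the written text alone; Figure 1 may show the intended logic, but the text would still need to match it. The correction should be made, but on this evidence the primary analysis is not at risk.

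**What to change.** Reconcile the treat sentence and the hold list in Protocol 3.2 with each other, with the re-check, continued-monitoring and growth-factor sentences, and with Figure 1, so that every combination of the three counts leads to exactly one action. A short table of the eight combinations, with one action entered against each and values exactly at a limit assigned to one side, would do this and could be checked at a glance. The same edit should say whether the rising-platelet condition at the re-check is meant to apply to a patient held only for a white-cell result.

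The investigators decide the clinical content; no rule is proposed here. The cost is a wording clarification in 3.2 and, if needed, in Figure 1. There is no data or analysis cost.
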